7.0 Study Procedures

Visit 1

Visit 1 procedures may take place over a single visit or may be broken up into multiple visits for ease of scheduling. In addition, some procedures may be carried out remotely to limit in-person interactions and reduce infection risks associated with COVID-19. For remote participation, the order of Visit 1 procedures (following informed consent) may be altered. All in-person study procedures will take place at Goodman Hall. For all visits, we will follow up-to-date IU and IU

Health safety guidelines, which may require children and parents to wear masks while in Goodman Hall.

The consent and assent procedures will be carried out prior to any study procedures. These may be carried out in person or remotely. Parents will provide written consent for their own and their child's participation. Children will provide written assent. For participants conducting the process in person, these forms will be presented in a private room to both parents and children together, and they will be given the opportunity to ask investigators any questions they may have. For participants and parents undergoing the process remotely, they will be sent a link to a REDCap survey. The person obtaining consent will conduct the consent and assent processes over the phone or video link (e.g., Zoom) while parents and children view documents electronically. All signatures will be obtained and recorded electronically and parents will be sent a copy of all signed documents via email or regular mail, as preferred.

Following the consent/assent process, we will collect personal information, including parent and child names, dates of birth, and the child's birthplace. This information will be maintained on a secure REDCap database, separate from personal health information and research databases. If the REDCap database is not available, we will take the information on a paper form, which will be shredded after entering the information into REDCap.

At the beginning of each remote study visit, the researcher will confirm the exact location of the subjects for safety purposes. If this is the same as the address provided on the form, that will be noted. If not, the subject's address will be written on paper or a white board and will be shredded after the visit.

Parents and child participants will undergo a semi-structured clinical interview, the **K-SADS-PL**, with a trained clinician, social worker, or clinical graduate student. This interview may be conducted in-person or remotely and may be scheduled on a separate day if necessary. This process is started by the completion of the **DSM-5 Self-Rated Level 1 Cross-Cutting Symptom Measure** questionnaire, which asks about the presence of child mental health symptoms over the previous two weeks. The interview allows the clinician to complete a diagnostic checklist. Parent(s) will be informed about results of the K-SADS clinical interview after it has been completed. If follow-up treatment is desired, we will provide information about local mental health treatment options. If requested, a brief written summary will be provided.

After the interview, in-person subjects will be given a short break. Snacks and small trinkets (~\$1) may be given to the child to help motivate them and maintain attention. These may also be given out at Visits 2 and 3.

Parents and children will also complete surveys. Survey questions will be presented and recorded via REDCap or the IU Qualtrics system, an online survey system. For remote participation, these surveys can be completed prior to the K-SADS-PL clinical interview. Prior to the clinical interview, the DSM-5 Self-Rated Level 1 Cross-Cutting Symptom Measure will be administered electronically. For in-person visits, both parents and children will complete surveys via electronic tablets (paper copies of surveys will be used if tablets are not functioning properly). Paper forms will be provided only if the electronic system is not working.

Children will first complete a practice survey to become familiar with the mechanics of using the tablet to answer questions. This practice will consist of all question types found in the surveys below.

Children will then complete the following surveys, expected to last 30 minutes in duration:

1. A child version of the **Interpersonal Reactivity Index (IRI)**, which provides subscales for Perspective Taking, Fantasy, Empathetic Concern, and Personal Distress.
2. **NIH Toolbox Perceived Hostility, Perceived Rejection, and General Life Satisfaction Fixed Forms**
3. The **Inventory of Callous-Unemotional Traits**, a 24-item questionnaire to provide an assessment of the child's callous and unemotional traits among antisocial youth.
4. **Media Exposure Questionnaire**. This questionnaire is a modified version of the Media Exposure Measure, which quantifies the child's television, video game and VR exposure.
5. **Virtual Reality Experience Survey**, which quantifies how much previous experience the child has had using virtual reality and specifies how often the technology was used for certain activities.
6. **Video Game Motivations and Desires**. This 30-item survey measures children's reasons for playing video games, based on the GAMES survey of video game motives and preferences.
7. **UPPS-P Impulsive Behavior Scale**. This 20-item self-report measures personality traits that lead to impulsive-type behavior.

For in-person participation, children will complete the K-BIT-2 IQ test⁴⁵ upon completion of surveys. If surveys are completed remotely, this IQ test will be conducted during the in-person portion of Visit 1.

Parents will complete separate surveys. These surveys include the following:

1. **Demographics** – Parents will report background information on their child and the family, including age, sex, grade, handedness, and parental income and employment. This questionnaire also collects information on the child's medical history, primarily focusing on mental health treatment.
2. **Parent Pubertal Development Scale**, which measures the child's stage of development.
3. **NIH Toolbox Emotion Battery Ages 8-12 Parent Report**, which includes surveys assessing the child's Positive Affect, General Life Satisfaction, Emotional Support, Friendship, Loneliness, Perceived Rejection, Perceived Hostility, Self-Efficacy, Sadness, Perceived Stress, Fear, and Anger
4. The **Outburst Monitoring Scale (OMS)**,⁴⁶ which measures the child's verbal, physical, property, and self-directed aggression.
5. **Media Exposure Questionnaire**. This questionnaire is a modified version of the Media Exposure Measure, which quantifies the child's television and video game exposure.
6. **Virtual Reality Experience Survey**, which quantifies how much previous experience the child has had using virtual reality and specifies how often the technology was used for certain activities.
7. **Family Environment Scale (FES): Short Version**,⁴⁷ a 9 item questionnaire designed to assess personal relationships and the overall social environment of a family through three categories: interpersonal relationships, growth, and organization/structure.

8. The **Sleep Disturbance Scale for Children**,⁴⁸ a 27 item questionnaire used to gauge overall sleep habits and disorders in children. This scale uses five subdomains: initiating and maintaining sleep, breathing, arousal, sleep wake transitions, excessive somnolence and hyperhidrosis.

9. The Indiana Institute of Biomedical Imaging Sciences (IIBIS) **MRI Safety Screening Form** to confirm that there are no MRI contraindications (paper only)

Remaining procedures require in-person participation. Participants will practice using the Oculus Quest VR headset, which includes goggles and headphones. As part of this practice, participants will develop their virtual avatar, which will be used during virtual scenarios at the next visit and may be provided to them prior to the second visit. To increase identification with their virtual self, participants will be directed to create a virtual avatar that best resembles them (sex, hair color/length, skin tone, choice of t-shirt). Following this use, child participants will complete the **Simulation Sickness Questionnaire**,⁴⁹ which quantifies physical symptoms such as general discomfort, nausea, and dizziness. If there is time, parents may also be provided the opportunity to wear the headset.

Lastly, participants will visit and lay in a mock scanner, to increase their comfort with the MRI scanner. The mock scanner provides a similar environment and can play similar noises as the real scanner.

If there are concerns about potential signal loss from orthodontics or implants that are MRI-safe, the participant may also receive a brief (roughly 10 minute) MRI scan to assess the extent of signal loss in the brain.

For all parent and child surveys, subjects may be asked to retake all or parts of these surveys where there may have been errors (e.g., technical difficulties or noncompliance), as determined by the research team.

If the VR practice or avatar creation could not be completed during Visit #1, it can be completed at the beginning of Visit #2.

Visit 2

Participants will undergo an MRI scan that will last about 1 hour. Prior to the scan, the parent and child will complete the Indiana Institute of Biomedical Imaging Sciences (IIBIS) **MRI Safety Screening Form** to confirm that there are no MRI contraindications. They will also complete the **Medication Log** form to indicate what medications or caffeine the subject had taken that day. This information will also be provided to parents during the reminder call or email for Visit 3, with a request that the same substances be utilized at Visit 3 if possible.

Participants will also see examples of stimuli that they will view during the scan and be instructed on what the MRI task will entail. They will practice button-press tasks as well.

MRI scans will take place on a research-dedicated 3T Siemens Magnetom Prisma MRI scanner at Goodman Hall. First, we will conduct a 3D magnetization prepared rapid gradient echo (MPRAGE) scan for individual anatomical reference, comprised of 160 sagittal slices with 1.0x1.0x1.2 mm voxel dimension. In the scanner, images will be presented via E-prime

software and back-projected to participants. Functional scans will be acquired using T2*-weighted gradient spin echo-planar imaging (EPI) sequence with TR/TE 1200/29 ms for 54 axial slices and voxel size of 2.5x2.5x2.5 mm.

The fMRI task employs a paradigm that has compared self vs. other perspective taking in the response to painful stimuli.¹⁸⁻²¹ A mixed block fMRI design will be used, with two 8-minute runs of our task. There are four conditions: self pain, self no pain, other pain, and other no pain. Each block (40sec duration) will be either "Self" or "Other," as indicated by task instructions prior to the block ("Imagine these situations are happening to you/him/her) and an image of the virtual avatar (virtual self or virtual counterpart; image remains in corner throughout block). Within the block, participants will be shown Pain images (e.g., hand slammed in door) and No Pain images (e.g., hand on door handle) (3 each/block; 2sec duration; jittered interstimulus interval 2-5sec).¹⁸⁻²⁰ There will be 6 blocks of each type during both 8-minute runs (96 total trials/run), with block order pseudorandomized across participants.

An additional task will present subjects with child faces with different emotional faces and ask them to respond to specific questions that probe emotion recognition, empathy, or the sex of the face.

After the MRI, the subject will be presented with a series of images. They will then determine which of the images they saw while completing the tasks in the MRI. This task measures how well subjects were attending to stimuli during the brain scan.

Visit 3

Participants will take part in the VR task with the Oculus Quest VR headset. We will fit the headgear to the child and ensure that it is comfortable. Subjects will remain seated while interacting with the virtual world and use hand-held controls to move or control objects. Subjects can turn their head to look in any direction in the virtual world. Using state-of-the-art 'Oculus Touch' hand-held controllers that react to hand movements, the user will be able to move and interact with virtual objects and characters. Headphones play auditory stimuli.

Children will first explore the virtual cafeteria for three minutes to allow them to understand hand controls and become acquainted with the environment before starting the task scenarios. They may ask questions and talk with investigators during this time, who will ensure that subjects are able to use controls and move around in the environment properly.

The virtual environment is a school cafeteria setting. Following practice, participants will take part in three scenarios in the school cafeteria. Each scenario will last up to two minutes. In two scenarios, after the subject hears the school bell ring, the goal is to place trash on their cafeteria tray and take the tray to the trash. In a third scenario, the subject is directed to clean up the mess at their table. Once the task is complete, the scenario will be complete. In each scenario, virtual characters will populate the environment to make it more realistic, including some characters (students) who will also be returning their trays. However, the social environments will differ, and each scenario includes a virtual counterpart that interferes with the goal.

After each scenario, children will remove the headset and complete questions via electronic tablet. First, they will complete our **VR Perspective Taking Scale**, which assesses how well they understand the virtual counterpart's perspective. Next, they will complete a question for the **Acknowledgement of Other Perspective Scale**, which reflects the relative importance given to the perspective of the participant and the virtual counterpart.

They will also complete a **Post-scenario Survey** regarding how they interpreted the intentions of the virtual counterpart (Were any of the characters trying to be nice to you? Were any of the characters trying to be mean to you?) and real-life responses (Would you be mad if this happened in real life? Would you try to hit other characters if this happened in real life?). Responses will be provided on a continuous sliding scale from 0 to 100 with labeled endpoints. We will also quickly assess current mood state (happy, sad, stressed, frustrated, calm) on sliding scales and complete the **Simulation Sickness Questionnaire** and a **VR Usability Survey**.

Following completion of each scenario, subjects will then experience the scenario again. Each subject will be randomly assigned to the (a) Alternate Perspective or (b) Control Perspective. In the Alternate Perspective condition, participants will experience the scenarios again from the virtual counterpart's perspective within the VR system. The Control Perspective will repeat the initial interaction from the same perspective. After each scenario, participants will answer questions identical to those after initial scenarios: the **VR Perspective Taking Scale** and the **Acknowledgement of Other Perspective Scale**, as well as questions about character intent, real-life responses, mood, the **Simulation Sickness Questionnaire**, and **VR Usability**.

If errors with the VR technology are observed, subjects may restart the scenarios and subsequent surveys.

Parents will also once again complete the Indiana Institute of Biomedical Imaging Sciences (IIBIS) **MRI Safety Screening Form** and the **Medication Log**.

Participants will be instructed about the MRI task and will briefly practice again. Participants will then undergo an MRI scan for about 1 hour. This scan may not be performed if the previous scan (at Visit 2) was not completed successfully. This scanning session will be identical to Visit 2, including an anatomical scan and functional scans in which participants will see images of painful and non-painful actions, under conditions where they are told to imagine scenes happening to themselves or the virtual counterpart, as well as the emotional face task.

After the scan, participants will be presented with images and asked to identify which ones they remember from the MRI scan.

Following the MRI scan, children will complete an end-of-study **Usability** and **Environmental Presence** survey, that asks additional questions about overall usability, environmental presence (how "real" the environment feels), and opinions on its helpfulness. Investigators will then answer any questions that they may have about their involvement or the VR scenarios.

At the beginning of each in-person visit, parents are to complete the **Parent/Guardian Safety Contact Sheet**. This asks for the parent/guardian's name and phone number where they can be reached for the duration of the visit. This form gets shredded after each visit.

Prior to receiving compensation for the visit, the parent and child will be asked briefly about real-life situations that prompted recent arguments. The responses will be recorded by the researcher and used to develop content for the next phase of research.

At the end of each visit, parents and children will then be compensated and thanked for their time. A school note will be provided upon request confirming the child attended our study visit.

Compensation

Participants will be compensated at the completion of each study visit. For remote participation, compensation will be provided via electronic gift cards. Children will receive \$75 for Visit 1 (\$25 for surveys, \$25 for K-SADS-PL, \$25 for VR practice/MRI mock scanner), \$100 for Visit 2 (including \$75 for MRI), and \$150 for Visit 3 (including \$75 for VR procedures and \$75 for MRI). Parents will receive \$25 for Visit 1. In addition, a parking voucher will be provided for each study visit. If a participant withdraws prior to completion of all visit procedures (including Visit 1 procedures scheduled on a separate day), they will be compensated only for tasks that have been completed. Parking will be compensated in full for each visit regardless of which tasks have been completed.

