3.0 Outcome Measures

Primary Outcome Measure: VR Perspective Taking Scale

This scale measures the degree to which participants understand the perspective of their virtual counterpart. It will be completed after each VR scenario, both pre- and post-intervention. Each participant's change score will be as Post-treatment (Endpoint; following all VR) vs. Pre-treatment (Baseline; after first scenario). The Cohen's d effect size will be calculated using the difference in mean change scores between treatment and control conditions (e.g., $[\text{Mean}_{\text{Enriched Post-Pre}} - \text{Mean}_{\text{Control Post-Pre}}] / \text{SD}_{\text{pooled}}$), resulting in an effect size measurements for both scales with each treatment condition.

Primary Outcome Measure: Acknowledgement of Other Perspective Scale

This scale allows participants to rate the relative importance of the virtual counterpart's perspective with a scenario-specific question. It will be completed after each VR scenario, both pre- and post-intervention. Each participant's change score will be as Post-treatment (Endpoint; following all VR) vs. Pre-treatment (Baseline; after first scenario). The Cohen's d effect size will be calculated using the difference in mean change scores between treatment and control conditions (e.g., $[\text{Mean}_{\text{Enriched Post-Pre}} - \text{Mean}_{\text{Control Post-Pre}}] / \text{SD}_{\text{pooled}}$), resulting in an effect size measurements for both scales with each treatment condition.

Primary Outcome Measure: Neural response to Self vs. Other Pain

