This is an fMRI measure of brain function while imagining pain happening to oneself or the virtual counterpart. Following standard preprocessing of fMRI data, we will calculate the regression coefficient for each stimulus type (Self Pain; Self No Pain; Other Pain; Other No Pain). We will extract mean activity from a priori regions-of-interest (ROIs), established as 10-mm radius spheres around MNI coordinate peaks in dACC (-2,33,40) and anterior insula (left: -40,22,0; right: 39,23,-4), which were identified as key regions for pain response in a recent meta-analysis. Brain activity will be quantified by contrasting self-perspective pain (Self Pain vs. Self No Pain) with other-perspective pain (Other Pain vs. Other No Pain). Cohen's d effect size will be calculated separately for each treatment and each ROI. For more traditional statistical measures, a 2x3 (pain perspective condition by group) within-subjects ANOVA test will be performed on data from each ROI.

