5.0 Study Design

This project will examine how levels of a virtual reality treatment that provides users with the alternate perspective of an interpersonal interaction impacts psychological and neurobiological markers of perspective taking. Prior to Visit 3, participants will be randomly assigned to different VR perspective conditions, stratified by sex, presence/absence of ADHD diagnosis, and ODD/CD diagnosis, via an a priori randomization chart. An equal number of youth will be randomly assigned to either the alternate perspective condition or control condition. Assignment will be sealed for the experimenter until immediately prior to Visit 3 (for visit preparation, experimenter must be unblinded). Visits 1 and 2 will be identical for both groups. At Visit 3, the initial VR scenarios and assessments will be identical. The participant will then re-experience the VR scenarios depending on their assigned condition. Additional VR assessments and the MRI scan will be identical for both groups.

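### Does the mismatch between 96 stated and 72 derived trials per fMRI run call for a change to the plan?

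*Combined protocol and SAP*

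**What the plan says.** Section 7.0, Visit 2, sets out the task in one paragraph. On runs: "A mixed block fMRI design will be used, with two 8-minute runs of our task". On blocks: "Each block (40sec duration) will be either" Self or Other. Pain and No Pain images are mixed within every block, with this timing: "3 each/block; 2sec duration; jittered interstimulus interval 2-5sec". On totals: "There will be 6 blocks of each type during both 8-minute runs (96 total trials/run". Task instructions are shown before each block. No other section gives a block, image or trial count.

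The task feeds the third primary outcome in section 3.0, "Primary Outcome Measure: Neural response to Self vs. Other Pain", for which "we will calculate the regression coefficient for each stimulus type (Self Pain; Self No Pain; Other Pain; Other No Pain"). Section 7.0, Visit 3, repeats the scan: "This scanning session will be identical to Visit 2". Section 5.0 says of the two arms: "Additional VR assessments and the MRI scan will be identical for both groups".

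**The concern.** The trial count is a basic design figure for an fMRI task, and this one stands beside the inputs from which it should follow. Those inputs give 72 per run against a printed 96, so the derived count is three quarters of the stated one. Because the Visit 3 session repeats Visit 2, the discrepancy covers both scans of a primary outcome.

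The number of trials per condition bears on how precisely each child's condition coefficients are estimated. Someone replicating or reporting the task from this text could not tell whether each condition had 36 or 48 trials per scan. If the count also fed the power calculation or an analysis rule, the slip would carry further.

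**Working it through.** **Inputs (section 7.0, Visit 2).** Two block types; 6 blocks of each type; 3 Pain + 3 No Pain = 6 images per block; blocks of 40 s; runs of 8 min = 480 s; images of 2 s; interstimulus interval (ISI) 2–5 s, mean not given; stated total 96 trials per run.

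**Attempt to reproduce 96.** Trials per run = blocks per run × 6 images; time per run = blocks per run × 40 s.

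| Reading of the block count | Blocks per run | Trials per run | Time per run |
|---|---|---|---|
| 6 Self + 6 Other in each run | 12 | 12 × 6 = 72 | 480 s |
| 6 Self + 6 Other over both runs | 6 | 6 × 6 = 36 | 240 s |
| 6 for each of the four conditions, in each run | 24 | 24 × 6 = 144 | 960 s |
| 6 for each of the four conditions, over both runs | 12 | 12 × 6 = 72 | 480 s |

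None gives 96. The last two readings also conflict with Pain and No Pain images sharing a block. Taking 96 as the total for both runs needs 96/6 = 16 blocks, or 8 per run (4 per type, 320 s), against the stated 6 per type. The first row is the natural reading, since its 12 × 40 s fills the run.

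**What would give 96 per run.**

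- 12 blocks with 96/12 = 8 images each, that is, 4 of each kind. One printed figure changes.
- 96/6 = 16 blocks of 6 images. At 40 s these take 640 s, more than the run, so block length would have to fall to 480/16 = 30 s. Two printed figures change.

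**Does the timing show which figure is wrong?** The product 12 × 40 s = 480 s does not involve the number of images, so it fits 6 or 8 per block equally well. The mean ISI that would fill a 40 s block is:

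- 6 images, interval after the last: (40 − 12)/6 = 4.67 s; no interval after the last: (40 − 12)/5 = 5.6 s, outside the stated range.
- 8 images, interval after the last: (40 − 16)/8 = 3.0 s; no interval after the last: (40 − 16)/7 = 3.43 s.

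Assume instead a mean ISI at the midpoint, (2 + 5)/2 = 3.5 s:

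- 6 images take 12 + 6 × 3.5 = 33 s or 12 + 5 × 3.5 = 29.5 s, leaving 7 to 10.5 s of the block unused.
- 8 images take 16 + 8 × 3.5 = 44 s or 16 + 7 × 3.5 = 40.5 s, slightly too long.

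The instructions shown before each block need time as well, and twelve full 40 s blocks leave none unless the instructions fall inside the 40 s. Spare time in a six-image block could hold them; eight images with a mean ISI near 3 s would also be workable. The timing does not decide between the two.

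**Size of the gap.**

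| | Derived | Stated, or following from 96 |
|---|---|---|
| Trials per run | 72 | 96 |
| Per condition per run | 72/4 = 18 | 96/4 = 24 |
| Per scan (two runs) | 144 | 192 |
| Per condition per scan | 36 | 48 |

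**Where the count is used.** Section 3.0 computes one coefficient per condition, extracts region means and contrasts them. Section 12.0 bases power on 20 children per group, a pre/post correlation of 0.6 and an effect size of 0.73 for a behavioural rating. Its mixed models, the region-of-interest ANOVA, the whole-brain ANOVA and the exploratory regressions contain no trial count. There is no plan rule, such as a minimum number of usable trials, that refers to 72 or 96.

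**The case for a change.** The best case for acting is that the error is certain, sits in the procedure for a primary outcome, applies at both scans, and could be put right by one look at the task program and one edited sentence. A protocol should let a reader reconstruct the task, and this paragraph does not.

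All of that is accurate as a point about the text. What it lacks is a consequence for the trial. The number of images a child sees is fixed by the programmed task. Correcting the sentence would make the text agree with that program; it would not add or remove an image, alter a coefficient or change a comparison. Precision within each child depends on the trials actually run, and since both arms have the same scan, any effect of the count falls equally on both. A first-level fMRI model is ordinarily built from the stimulus times of the presented task, so an analyst would use the real count without consulting the protocol's total.

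The case that 72 must be the intended figure is weaker than it first appears. It rests on block count, block length and run length agreeing with one another, but those three say nothing about images per block.

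**Conclusion.** The paragraph contradicts itself: its own inputs give 72 trials per run where it prints 96, a gap of 24 per run, or 36 versus 48 per condition per scan. Either the total or the number of images per block is probably the misprint, and the document does not settle which. This is a clerical slip. The sample size, power, contrasts, models and between-arm comparison are the same whichever figure is right, so no change to the plan follows. Whoever next edits or reports the task can take the count from the program.

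This rests on two assumptions: that the programmed task is coherent in itself, and that it is the same program for both arms and both visits, as sections 5.0 and 7.0 state. The midpoint ISI of 3.5 s is used only for illustration; the conclusion does not depend on it.
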